## **10.0 RECORDS TO BE KEPT**

CRFs will be provided for each subject via the AMC AdvantageEDCSM Internet Data Entry System upon enrollment. Subjects must not be identified by name on any study documents. Data will be recorded on the CRFs using the unique subject identification number assigned at registration. Sample CRFs will be available on the AMC Operations Center website.

## **11.0 ROLE OF DATA MANAGEMENT**

### **11.1 CRF Instructions**

Instructions concerning the recording of study data on CRFs will be provided by the Operations Center.

### **11.2 Data Quality**

It is the responsibility of the AMC Operations Center to assure the quality of data for the study. This role extends from protocol development to generation of the final study database.

## 12.0 STATISTICAL CONSIDERATIONS

### 12.1 Sample Size Estimation

The response rate (CR + PR) to imatinib in the pilot study is 50% to date. It is well known that some patients have regression of their KS after beginning HAART therapy. In order to minimize the effect of HAART being a potential confounding factor in response rates, recent studies have required patients on HAART to be on stable regimens for 12 weeks prior to initiation of treatment. Recent results from two placebo-controlled studies suggest as many 20% of responses in KS clinical trials may be delayed responses to HAART alone.[19, Walmsley, 1999 #136] Simon's two-stage design will be used to test the null hypothesis that the response rate (CR + PR) is 20% against the alternative that it is 50% at the one-sided 0.05 significance level with power of 0.90. Ten patients will be enrolled in the first stage. If no more than two patients respond, then the study will be stopped. If at least three patients respond, then the study will enroll up to a total of 22 patients. If no more than seven patients respond, the drug will be considered ineffective. If at least eight patients respond, the null hypothesis will be rejected in favor of the alternative hypothesis. The probability of early termination of the study is 0.68.

In our original estimate, we assumed a drop out rate of 10-15% based on our experience in the pilot study and calculated a sample size of 25 patients. However, we have had a higher drop out rate. Consequently, based on a drop out rate of 20-30%, we plan to roll a total of 30 patients to have 22 patients evaluable for response.

In the pilot study, we found that decreasing the dose of imatinib by 33% (600 mg/day to 400 mg/day) dramatically decreased the incidence of AEs. This dose reduction should reduce the steady state concentration of imatinib and its metabolite by 1 standard deviation of steady state plasma concentration, assuming constant clearance. This observation suggests a change in the plasma concentration imatinib and/or its metabolite of 1 standard deviation would be significant in our patient population. Based on this assumption, a PK sampling of 12 patients will provide a power of 88% to detect a 1 standard deviation change in the steady state level of imatinib and its metabolite with a type I error of 0.05 using a two-sided paired t-test.

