## **SITES PARTICIPATING IN AMC # 042**

**This trial is open to all AMC sites for subject accrual.**

## SCHEMA

- TITLE:** A Phase II Trial of Imatinib Mesylate (Gleevec®) in Patients with HIV Related Kaposi's Sarcoma.
- DESIGN:** Open-label, Phase II Study.
- SAMPLE SIZE:** A maximum of 30 subjects will be enrolled.
- POPULATION:** HIV infected subjects with biopsy proven Kaposi's sarcoma (KS) involving skin, lymph nodes, oral cavity, GI tract and/or lungs. GI and pulmonary involvement must be asymptomatic or minimally symptomatic and not require systemic cytotoxic therapy.
- REGIMEN:** Patients will be taking Gleevec 400 mg orally once a day.
- DURATION:** Patients will continue on study protocol as long as their KS is stable or responding for up to 6 months. If a patient has been on study for at least 3 months with stable disease and without any toxicity, their dose may be increased to 600 mg/day. Patients who are responding or have stable disease at 6 months may continue on study for an additional 6 months. Protocol treatment will be discontinued if the patient develops tumor progression, unacceptable toxicity or develops one of the protocol defined reasons for treatment discontinuation.
- EXPECTED ACCRUAL:** A maximum of 30 subjects over 12 months.
- PRIMARY ENDPOINTS:** Evaluation of clinical response.
- SECONDARY ENDPOINTS:** Evaluation of inhibition of PDGF-R as determined by immunohistochemistry.
- Evaluation of cytokine profiles pre and post imatinib therapy.
- Evaluation of pharmacokinetic profile of imatinib and antiretrovirals in HIV patients.
- Evaluation of mechanisms of primary and secondary resistance to imatinib therapy.
- Evaluation of viral transcription profile of KSHV.

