#### 1.1.5 Summary of Pilot Trial Data

Based on the in vitro data supporting the role of c-kit and PDGF-R activation in KS, a pilot trial at Beth Israel Deaconess Medical Center in Boston, MA was initiated. Ten patients who were on stable doses of highly active anti-retroviral therapy (HAART) and who had failed first line KS therapy have been enrolled. The primary goal of the trial was to confirm the expression of c-Kit and PDGF-R in KS lesions and to determine the activation status of the c-Kit and PDGF receptors in KS at baseline and after 4 weeks of treatment with imatinib. The secondary goal was to collect data on the tolerability and clinical efficacy of imatinib in HIV-related KS. Patients were treated with imatinib 300 mg orally, twice daily with dose reduction permitted for toxicity. At baseline and at 4 weeks, patients had tumor measurements, a 4 mm punch biopsy of a representative lesion and a plasma sample. Patients with a response at 4 weeks were allowed to continue therapy until disease progression. AIDS Clinical Trial Group (ACTG) criteria were used for clinical response. Five of 10 patients had at least a partial response (PR) by clinical criteria after only 4 weeks of imatinib therapy. Three of 10 patients had stable disease. The median duration of therapy was 7 weeks (range 4 to 26 weeks). The majority of patients required dose reduction from 600 mg daily to 400 mg daily after 4 weeks of therapy. One patient had Grade 4 neutropenia that recurred after dose reduction. Five patients had diarrhea (three exhibited Grade 3, and one Grade 4) that resolved with drug withdrawal. Two of these five patients with diarrhea had diarrhea at baseline. Diarrhea returned with drug re-challenge, but was manageable with over-the-counter anti-diarrhea medications. No significant change in CD4 counts or viral load was noted during therapy.

We hypothesize that the high rate of GI toxicity that was observed may be related to a PK interaction between imatinib and HAART. Imatinib is a substrate for the cytochrome p450 isoenzymes, cyp3A4 and cyp2D6. All of the protease inhibitors (PIs) in clinical use at the time of this study, which includes, amprenavir, indinavir, lopinavir, nelfinavir, ritonavir, saquinavir are cyp3A4 inhibitors with ritonavir inhibiting cyp2D6 to a lesser extent. Diarrhea is a side effect common to all of the PIs. The other class of antiretrovirals shown to affect the

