## **4.2 Evaluations During Treatment**

Evaluations may occur up to 7 days before or after the end of the study visit indicated. Each cycle will be 28 days. Evaluations will continue as outlined below. Patients on the 6-month extension arm will also follow the outline below.

- 4.2.1 Clinical assessment on Days 1, 8, 15, 29 and then every 28 days thereafter, to include an assessment of the following, at every visit (unless otherwise specified):
  - 4.2.1.1 KS tumor assessment at baseline (to be performed on Day 1 prior to receiving study medication, but no earlier than 2 weeks prior to initiating treatment) Day 29, Day 56 and every 2 months thereafter (see Section 4.1.6).
  - 4.2.1.2 A complete physical exam including: vital signs, weight, Karnofsky performance status (Appendix IV) and toxicity evaluation (Days 8, 15, 29 and then every 28 days thereafter).
  - 4.2.1.3 Signs and Symptoms Review.
  - 4.2.1.4 Complete blood count with differential and platelets.
  - 4.2.1.5 Serum chemistries: liver enzymes (SGOT, SGPT, alkaline phosphatase), BUN, creatinine, electrolytes, amylase, bilirubin (direct and indirect, if total is elevated) and phosphate.
  - 4.2.1.6 Urine phosphate and urine creatinine for calculation of fractional excretion of phosphate ( $FE_{PO_4}$ ). [Fractional excretion of phosphate=(spot urinary phosphate/serum phosphate)/(spot urinary creatinine/serum creatinine) × 100].
    - 4.2.1.6.1 If  $FE_{PO_4} > 5\%$  or serum phosphate is low then 25-hydroxyvitamin D should be drawn at next visit or within 7 days (whichever is sooner).
  - 4.2.1.7 For women of childbearing potential: serum  $\beta$ -HCG at any time pregnancy is suspected.
  - 4.2.1.8 All HIV-related and AIDS-defining events (Appendix III) and concomitant medications.

- 4.2.2 CD4 count at baseline, Day 29 and every 3 months thereafter.
- 4.2.3 HIV-1 plasma RNA at baseline, Day 29 and every 3 months thereafter (to be evaluated at local institution).
- 4.2.4 HHV-8 Viral Load- Day 1 and Day 15 of cycle 1, and on Day 1 of cycles 3, 5, 7, 9, 11 (see Appendix XIII).
- 4.2.5 HHV-8 Viral Gene Expression- Day 1 and Day 15 of cycle 1, and on Day 1 of cycles 3, 5, 7, 9, 11 (see Appendix XIII).

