Accrual summaries for each AMC trial are updated nightly on the password-protected section of the AMC Web page. The progress of each AMC trial is reviewed regularly by the Protocol Chair and also by the appropriate disease-oriented Working Group during scheduled conference calls. For phase I dose escalation trials, dose escalation (or dose de-escalation) is based on the rules in the protocol and the Protocol Chair and Group Statistician determine whether these criteria have been met. For phase II trials, stopping the trial for toxicity or efficacy, or suspending enrollment pending observation of responses in a multi-stage phase II trial, is based on meeting criteria stated in the protocol, and the Protocol Chair and Group Statistician determine whether these criteria have been met.

For phase III trials, the AMC has formed an independent Data Safety and Monitoring Committee (DSMC). Voting members of the DSMC are physicians, statisticians, and a patient advocate. All voting members are from outside the AMC. Non-voting members are the NCI scientific project officers and an NCI statistician. The AMC Data Safety and Monitoring Committee reviews AMC phase III studies in accordance with the National Cancer Institute's Policy for Data Safety and Monitoring. Confidential reports of all phase III trials are prepared by the AMC Group Statistician with support from the AMC Operations and Data Management Center. A written report containing the current status of each trial monitored, and when appropriate, any toxicity and outcome data, are sent to DSMC members by the AMC Operations and Data Management

Center allowing sufficient time for DSMC members to review the report prior to the meeting. This report addresses specific toxicity concerns as well as concerns about the conduct of the trial. The report may contain recommendations for consideration by the DSMC concerning whether to close the trial, report the results, or continue accrual or follow-up.

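### Section 12.1 sets the Simon boundaries on 10 and 22 patients enrolled, yet the trial enrols 30 to obtain 22 evaluable; the stated power is assured only on the evaluable count

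*Combined protocol and SAP*

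**What the plan says.** Section 12.1 uses a Simon two-stage design for a response rate (CR + PR) of 20% against 50%, one-sided 0.05, power 0.90. Stage 1 reads: "Ten patients will be enrolled in the first stage. If no more than two patients respond, then the study will be stopped". With at least three responses, "then the study will enroll up to a total of 22 patients"; eight or more responses reject the null hypothesis. The stated probability of early termination is 0.68.

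The following paragraph of the same section says that "based on a drop out rate of 20-30%, we plan to roll a total of 30 patients to have 22 patients evaluable for response". The Schema agrees with the larger figure: "A maximum of 30 subjects will be enrolled".

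Appendix XVI refers the stopping decision back to this text. It says that "suspending enrollment pending observation of responses in a multi-stage phase II trial, is based on meeting criteria stated in the protocol", and that "the Protocol Chair and Group Statistician determine whether these criteria have been met".

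Section 9.1 defines CR, PR, stable and progressive disease but not who is evaluable. Section 12.2 names no denominator for the response rate or its confidence interval. Appendix IX, A.4 classes stable disease and progression as non-response, but for the correlative aims.

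**The concern.** A total of 22 enrolled and a total of 30 enrolled cannot both be the trial size. The dropout paragraph moves the final count from enrolled to evaluable and leaves stage 1 on ten enrolled. The people who decide on early stopping are told to use the protocol's criteria, and those criteria give an enrolled count. By the plan's own 20-30% dropout, two or three of the first ten would be expected to drop out. If they occupy stage 1 places without a chance to respond, an active drug is stopped more often than planned.

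The text also gives no rule for a final count other than 22, and it leaves evaluable open in a single-arm, open-label trial. Patients who leave early without a response could be taken out of the denominator after their outcome is known, which would push the response rate up.

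**Working it through.** **Inputs.** From Section 12.1: rates 0.20 and 0.50; stop at 2 or fewer of 10; reject at 8 or more of 22; dropout d = 0.20 to 0.30; 30 enrolled. Assumptions of this check: patients drop out independently with constant probability d, and evaluable patients respond independently of dropout.

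**1. The plan's own figures.** P(reject) = sum over x = 3 to 10 of P(X = x) × P(Y ≥ 8 − x), with X ~ Bin(10, p) and Y ~ Bin(12, p).

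- p = 0.20: 0.2013 × 0.0726 + 0.0881 × 0.2054 + 0.0264 × 0.4417 + 0.0055 × 0.7251 + about 0.0008 = 0.049.
- p = 0.50: 0.1172 × 0.8062 + 0.2051 × 0.9270 + 0.2461 × 0.9807 + 0.2051 × 0.9968 + 0.1172 × 0.9998 + 0.0547 = 0.902.
- Early termination, P(X ≤ 2): 0.678 at p = 0.20 and 0.055 at p = 0.50.

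The design is correct when 10 and 22 are numbers of patients in whom the 20% and 50% rates apply.

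**2. Stage 1 on 10 enrolled, final test on 22 evaluable.** The number evaluable in stage 1 is M ~ Bin(10, 1 − d). If no dropout responds, stage 1 responders follow Bin(10, 0.5 × (1 − d)), that is, rate 0.40 at d = 0.20 and 0.35 at d = 0.30. Power is the average over M of the two-stage formula with M in place of 10 and 22 − M in place of 12.

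| Case, true rate 50% | Early stopping | Power |
|---|---|---|
| 10 and 22 evaluable (planned) | 5.5% | 0.902 |
| 20% dropout, no dropout responds | 16.7% | 0.804 |
| 30% dropout, no dropout responds | 26.2% | 0.716 |
| 20% dropout, half of dropouts assessable | 10.0% | 0.864 |
| 30% dropout, half of dropouts assessable | 13.0% | 0.837 |
| 50% is the rate per enrolled patient | 5.5% | no stage 1 loss |

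In the two cases where no dropout responds, alpha falls to 0.038 and 0.031, so the cost is power.

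**3. Final count other than 22**, stage 1 on 10 evaluable, cut 8 unchanged.

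| Evaluable | Alpha | Power |
|---|---|---|
| 19 | 0.022 | 0.808 |
| 20 | 0.030 | 0.850 |
| 21 | 0.039 | 0.881 |
| 22 | 0.049 | 0.902 |
| 23 | 0.060 | 0.917 |
| 24 | 0.073 | 0.927 |

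**4. What 30 enrolled covers.** 1 − 22/30 = 26.7%. At 30% dropout the expected number evaluable is 30 × 0.70 = 21, and 22/0.70 = 31.4, so 32 would be needed. With N ~ Bin(30, 1 − d), the chance of fewer than 22 evaluable is 13%, 33% and 57% at 20%, 25% and 30% dropout. The chance of fewer than 19 is 1%, 5% and 16%.

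**5. Early leavers counted as non-responders in both stages.** If every dropout is of this kind and 50% holds only among the rest, the rate in the counted patients is 0.40 or 0.35. The formula in step 1 then gives power 0.663 or 0.483.

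**The case against.** The natural reading of a Simon design is that both stages count evaluable patients. The second paragraph of 12.1 ties the 22 to evaluability, and Appendix XVI speaks of observed responses. The 50% alternative comes from the pilot, where "Five of 10 patients had at least a partial response", which is a rate per enrolled patient; on that basis stage 1 loses nothing. Assessed patients without CR or PR are already non-responders: response is defined as CR + PR, and Section 9.1.4 makes stable disease the residual class. Tumor assessments are due at "Day 29, Day 56 and every 2 months thereafter", at discontinuation (Section 4.3.5) and thirty days later (Section 8.0), so few patients may be truly unassessed. The existing cut holds alpha for any total of 22 or fewer. Thirty enrolled fits the middle of the dropout range (22/0.75 = 29.3). Finally, counting early leavers as non-responders can cost more power than the ambiguity itself.

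Much of this stands. The low power figures are the upper end of the loss, no new cut is needed for 19 to 21 evaluable, and the power cost of a strict definition must be stated. What it does not answer is that the text says enrolled for both stages, gives two incompatible totals and sends the stopping decision to that wording. Even on the evaluable reading, the term is undefined.

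**Conclusion.** The rule is wrong as written. Its boundaries and stated error rates are sound for 10 and 22 evaluable patients, but the words put them on enrolled patients, and applied that way the rule can miss its stated power. At 20% or 30% dropout, power lies between 0.90 (50% is a per-enrolled rate) and 0.80 or 0.72 (50% holds among evaluable patients, no dropout responds, and 22 evaluable are still reached). The documents do not say which case applies.

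Three stronger readings are tempting and not supported:

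- That the design arithmetic is wrong. It reproduces exactly.
- That the type I error is inflated. This needs more than 22 evaluable patients judged against cut 8. The text does not rule that out if all 30 are enrolled, but it does not require it, and the stated total of 22 points the other way. At 22 or fewer, alpha stays below 0.05.
- That the response rate will be biased upward. An open definition permits it, but the documents neither plan such exclusions nor allow their effect to be sized.

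Separately, the dropout allowance is overstated: 30 enrolled gives an expected 22 evaluable up to 26.7% dropout, not 30%.

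**What to change.** Amend Section 12.1:

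1. State that the boundaries apply to the first 10 and the first 22 evaluable patients in order of enrolment, with no more than 22 used for the decision. Reconcile the total of 22 with the 30 enrolled.
2. Define evaluable before results are reviewed, so that treated patients who leave for toxicity, progression or death without a documented response stay in the denominator. State that the 50% alternative is then a rate in that population, and give the power cost if it is not (0.66 or 0.48 in the extreme case of step 5).
3. State that cut 8 is kept if 19 to 21 patients are evaluable, with the attained alpha and power from step 3. Cuts for fewer than 19 are optional.
4. Restate the dropout allowance as up to about 26%.

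This is wording plus a short table and needs no new data, since the tumor assessments are already scheduled. The cost is that stage 1 may need about 13 to 15 enrolled patients before the decision (10/0.8 = 12.5; 10/0.7 = 14.3), and that the stated power and dropout allowance become less favourable.

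### Thirty enrolled patients support an expected 22 evaluable only up to about 26.7% dropout; at the stated upper bound of 30% the expected number is 21 and power is about 0.88

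*Combined protocol and SAP*

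**What the plan says.** Section 12.1 (Sample Size Estimation) sets out a Simon two-stage design. It tests the "null hypothesis that the response rate (CR + PR) is 20% against the alternative that it is 50" per cent, "at the one-sided 0.05 significance level with power of 0.90".

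The rule is as follows:
- Stage 1: "Ten patients will be enrolled in the first stage". "If no more than two patients respond, then the study will be stopped".
- Stage 2: "If at least three patients respond, then the study will enroll up to a total of 22 patients". "If at least eight patients respond, the null hypothesis will be rejected in favor of the alternative hypothesis".

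The next paragraph of Section 12.1 moves from evaluable to enrolled patients. Because dropout has been higher than first assumed, it says: "based on a drop out rate of 20-30%, we plan to roll a total of 30 patients to have 22 patients evaluable for response". It does not say which rate within the range produced 30. The Schema fixes the ceiling: "A maximum of 30 subjects will be enrolled".

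**The concern.** The sentence attaches one enrolment figure and one evaluable figure to a range of dropout rates. A reader will take it that 22 evaluable patients can be expected anywhere between 20% and 30%. At 30% that is not so, since 30 × 0.70 is 21.

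The number 22 matters because the decision rule and its operating characteristics were worked out for exactly 22 evaluable patients. With fewer patients and the same requirement of eight responses, the test is harder to pass and power falls below 0.90. Enrolment is capped at 30, so if dropout does reach the upper bound the missing patient cannot be replaced without amending the protocol. At stake is the accuracy of the sample-size statement at one end of its own range. The validity of the design is not in question.

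**Working it through.** **Inputs, all from Section 12.1 except the cap (Schema).** Null rate p0 = 0.20, alternative p1 = 0.50; stage 1 of 10 patients, stop at 2 or fewer responses; 22 evaluable in total, reject at 8 or more; dropout 20–30%; maximum enrolled 30.

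**1. Reproduce the design at 22 evaluable.** The probability of rejecting is the sum, over stage 1 responses x = 3 to 10, of P(X1 = x) × P(X2 ≥ 8 − x), with X1 ~ Bin(10, p) and X2 ~ Bin(12, p).

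- Early stopping under the null: P(X1 ≤ 2 | 0.20) = 0.678. The plan says 0.68.
- Type I error at p = 0.20: 0.0492. The plan says 0.05.
- Power at p = 0.50, with the terms for x = 3, 4, 5, 6, 7 and then x ≥ 8: 0.0945 + 0.1901 + 0.2413 + 0.2044 + 0.1172 + 0.0547 = 0.902. The plan says 0.90.

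All three stated figures are confirmed.

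**2. Expected evaluable patients from 30 enrolled**, 30 × (1 − d):

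- d = 20%: 30 × 0.80 = 24
- d = 25%: 30 × 0.75 = 22.5
- d = 30%: 30 × 0.70 = 21

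The break-even rate solves 30 × (1 − d) = 22, so d = 8/30 = 26.7%. That covers (26.7 − 20)/(30 − 20), about two thirds of the stated range.

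**3. Enrolment needed to expect 22 evaluable**, 22/(1 − d), rounded up:

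- d = 20%: 22/0.80 = 27.5, so 28
- d = 25%: 22/0.75 = 29.3, so 30
- d = 30%: 22/0.70 = 31.4, so 32

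Thirty is thus the size required at the midpoint of the range and two short of the size required at the top.

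**4. Operating characteristics at 21 evaluable.** Stage 1 and the final requirement of 8 responses are unchanged; stage 2 now has 11 patients, so X2 ~ Bin(11, p).

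- Power at p = 0.50, same terms: 0.0850 + 0.1818 + 0.2380 + 0.2039 + 0.1171 + 0.0547 = 0.881
- Type I error at p = 0.20: 0.039

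Relative to 22 evaluable, power falls by 0.902 − 0.881 = 0.021; relative to the stated 0.90, by 0.019. Type I error stays below 0.05. Lowering the requirement to 7 responses at 21 patients is not a remedy: power rises to 0.924 but type I error becomes 0.090.

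**The case against.** The best defence is that 30 is exactly the size needed at 25%, the midpoint of the range, and that Section 12.1 never says it was chosen for the 30% end. On that reading the sponsor sized for a central value, and the result at 30% is one patient short. This stands, and it limits the point to the part of the range above 26.7%. It does not remove the point, because the sentence names the whole range and gives 22 without qualification.

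The 0.90 also stands. It is stated for the 22-patient design, in a separate paragraph from dropout, and it is correct there.

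Three stronger readings are tempting, and the documents do not support them:

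- *That the trial will probably end with fewer than 22 evaluable.* Section 12.1 says only that dropout has been higher than assumed. It reports no observed rate, and 20–30% is a planning range. If dropout is assumed independent between patients, the chance of at least 22 evaluable among 30 is 0.87 at 20%, 0.67 at 25% and 0.43 at 30%. It falls below one half only above about 28.6%.
- *That low dropout inflates type I error*, because more than 22 patients would be analysed against a requirement of eight responses. The plan's target is 22 evaluable and 30 is a maximum, so accrual need not run on past 22. Nothing says that more would be analysed.
- *That there is no room anywhere in the range.* At 20% dropout 28 enrolled suffice, which leaves two places.

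**Conclusion.** The statement is wrong as written at the top of its range, and the error is minor. Thirty enrolled supports an expected 22 evaluable up to about 26.7% dropout. At 30% the expected number is 21, and exact power is about 0.88 instead of 0.90, with type I error controlled at 0.039. It would be wrong to conclude that the sample size fails over the stated range generally.

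The power figure assumes that ten evaluable patients enter stage 1, that the loss falls in stage 2, that the rule of eight responses is kept, and that the true response rate is 50%. The evaluable counts are expectations; the actual number will vary around them. Averaging power over that variation (independent dropout, evaluable total capped at 22) gives 0.896, 0.879 and 0.845 at 20%, 25% and 30%. These averages rest on assumptions that the documents do not make, so they serve as a sensitivity check and the conclusion does not depend on them.

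**What to change.** Replace the enrolment sentence in Section 12.1 with a statement along these lines: enrolling 30 patients is expected to give 24 evaluable patients at 20% dropout, 22.5 at 25% and 21 at 30%; an expected 22 is supported up to about 26.7% dropout; with the stated decision rule, power is 0.90 at 22 evaluable and about 0.88 at 21.

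The cost is an edit to one paragraph and a slightly less favourable power figure at the upper dropout bound. The maximum of 30, the stage sizes, the decision rule and the analysis all stay as they are, and no extra patients are needed.

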p450 system is the non-nucleoside reverse transcriptase inhibitors. Delavirdine is a cyp3A inhibitor while nevirapine is a cyp3A inducer, and efavirenz is a mixed cyp3A inducer/inhibitor. No relationship between any specific antiretroviral regimen and the incidence of diarrhea was observed in the pilot study.

Plasma samples were analyzed to determine levels of imatinib and its major active metabolite, CGP-74588 in the laboratory of [name]. At steady state the average imatinib concentration was 1,342 ng/mg (range 0 to 2,846 ng/mL) and CGP-74588 was 733 ng/mL (range 459 to 1,046 ng/mL) (n=9). These levels are low compared to CML patients on the same dose schedule, 2,939 ng/mg (range 2,009-3,497 ng/ml) and 733 ng/mL (range 459-1,046 ng/mL). Plasma concentrations of the antiretrovirals were not measured in the pilot study. Although this data suggest there is not inhibition of imatinib metabolism, the imatinib concentrations may not be representative of the steady state concentration. The samples were a random sample from Day 28, and by that time, all four patients with diarrhea had developed symptoms. The presence of the diarrhea could have affected the absorption of imatinib as well as patient adherence to the therapy. Because of the high potential of drug interactions in the HIV population the pharmacokinetics of imatinib in these patients still needs to be established.

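### Section 12.1 equates a 33% change in drug level with 1 SD without giving an SD, and applies the SD of concentrations to a paired t-test that needs the SD of within-patient differences

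*Combined protocol and SAP*

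**What the plan says.** Section 12.1 builds the PK sample size in four steps.

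1. From the pilot: "decreasing the dose of imatinib by 33% (600 mg/day to 400 mg/day) dramatically decreased the incidence of AEs".
2. Assuming constant clearance: "This dose reduction should reduce the steady state concentration of imatinib and its metabolite by 1 standard deviation of steady state plasma concentration".
3. From this it infers that "a change in the plasma concentration imatinib and/or its metabolite of 1 standard deviation would be significant in our patient population".
4. It concludes that "a PK sampling of 12 patients will provide a power of 88% to detect a 1 standard deviation change in the steady state level". The claim covers both parent drug and metabolite, and the test is two-sided and paired at the 0.05 level.

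No SD, CV, within-patient correlation or source accompanies these steps. The only concentration data in the protocol are in Section 1.1.5. For the parent drug in the HIV pilot it reports: "At steady state the average imatinib concentration was 1,342 ng/mg (range 0 to 2,846 ng/mL"). The metabolite in the pilot had a mean of 733 and a range of 459 to 1,046, with nine patients. For CML patients on the same dose schedule it gives imatinib 2,939 (range 2,009 to 3,497), and metabolite figures identical to those of the pilot.

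**The concern.** Constant clearance turns a one-third dose cut into a one-third fall in level. It says nothing about SDs. The fall equals 1 SD only if the SD is one third of the mean, for the parent drug and for the metabolite alike. The clinical meaning of the 88% therefore rests on a figure that the plan does not give.

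There is also a mismatch of scale. The SD named is that of plasma concentration, which describes spread between patients. A paired t-test is powered on the SD of the within-patient difference.

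At stake is how the PK result is read. Section 1.2.2.2 lists higher imatinib exposure caused by antiretrovirals as its first toxicity hypothesis, calls the pilot investigation inconclusive, and assigns the first 12 patients to the question. A reader may take 88% as the chance of detecting an exposure change of the size linked to toxicity, and so read too much into a non-significant comparison.

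**Working it through.** **Inputs.** Section 12.1: n = 12, two-sided alpha 0.05, paired t-test, change of 1 SD, dose cut of one third. Section 1.1.5: the means and ranges above. The pilot n = 9 is taken to apply to both analytes, and all levels are read as ng/mL.

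**1. The plan's own figure.** Power comes from the noncentral t distribution with 11 df and noncentrality d√12, where d is the change divided by the SD of the within-patient difference. At d = 1 power is 0.883, so the 88% reproduces.

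**2. What the equivalence requires.** One third of the mean = 1 SD means a CV of about 33%. For pilot imatinib that is an SD of 1,342/3 = 447.

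**3. Pilot imatinib.** The smallest sample SD compatible with the figures has one value at each extreme and the other seven equal:
- common value: (9 × 1,342 − 0 − 2,846)/7 = 1,318.9
- SD = √[(1,342² + 1,504² + 7 × 23.1²)/8] = 713, a CV of 53%
- one third of the mean = 447/713 = 0.63 SD at most

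A range-based SD, taking 2.970 SDs as the expected range of nine normal values, is 2,846/2.970 = 958 (CV 71%), and 447/958 = 0.47 SD.

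If the SD of the difference equals the SD of the level (correlation 0.5), power for a one-third change with 12 patients is 0.51 at SD 713 and 0.31 at SD 958.

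**4. CML imatinib.** One third of 2,939 is 980. The largest SD that the mean and range allow, with an n divisor, is √[(2,939 − 2,009)(3,497 − 2,939)] = √(930 × 558) = 720, so 980/720 = 1.36 SD or more. With an n − 1 divisor and an assumed n of 5 to 30 (none is given), the largest SD is about 767 and the ratio at least 1.28. The two imatinib data sets lie on opposite sides of 1 SD.

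**5. Metabolite.** One third of 733 is 244. The possible SDs run from 147 to 299, with a range-based value of (1,046 − 459)/2.970 = 198. The ratio is 1.66, 0.82 and 1.24 SD respectively, so 1 SD is compatible with these figures, if they are right.

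**6. Scale.** With equal variances on the two occasions, SD of difference = SD of level × √[2(1 − ρ)], where ρ is the within-patient correlation. The two SDs agree only at ρ = 0.5. Power with 12 patients:

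| ρ | change of 1 SD of level | change of 0.63 SD of level |
|---|---|---|
| 0 | 0.61 | 0.29 |
| 0.3 | 0.76 | 0.39 |
| 0.5 | 0.88 | 0.51 |
| 0.75 | 0.99 | 0.80 |
| 0.9 | >0.99 | 0.99 |

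**The case against.** The strongest reply is that Section 12.1 contains no miscalculation: it calls a 1 SD change significant, powers for 1 SD, and 88% is right if that SD is the SD of the difference. This stands. The fault lies in the link from 33% to 1 SD and in which SD is named.

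A second reply concerns the pilot data. Section 1.1.5 itself warns that these levels may not represent steady state: they were random Day 28 samples, possibly affected by diarrhea and adherence, and Section 1.1.5 also says that dose reduction was permitted. The reading of 0 weighs heavily. If there was one zero and it is dropped, the other eight average 12,078/8 = 1,510, the smallest possible SD is 540, and one third of the mean (503) is up to 0.93 SD, with power up to 0.84 at correlation 0.5. This also stands.

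A reader might therefore be tempted to infer that power for a one-third imatinib change is about one half at best. The documents do not support that. It fixes the correlation at 0.5, uses samples that the protocol qualifies, and takes the SD at the pilot dose. If the SD scales with dose to 400 mg/day (713 × 2/3 = 475), the same change is up to 447/475 = 0.94 SD and power up to 0.84. On the CML figures, with correlation 0.5, power is about 0.98 or more.

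Lastly, Section 12.2 lists only summary statistics for PK, and Section 4.2.7 compares with historical volunteers, so the paired test may never be reported. That lowers the stakes but leaves the sample-size justification in 12.1 unsupported.

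**Conclusion.** The point holds as a gap in justification plus a mismatch of scale, on a secondary objective. The CV of about 33% that the equivalence needs is unstated and unsourced. Neither imatinib data set supports it: at most 0.63 SD in the pilot (an arithmetic bound given n = 9), about 1.3 SD or more in the CML patients (assuming at least 5 of them). The pilot figures do not establish the true ratio at steady state.

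Read as 1 SD of plasma concentration, as the text has it, the 88% becomes 0.61 to 0.99 for correlations from 0 to 0.75. This result does not depend on the pilot data; it assumes equal variances on the two occasions.

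Power of 0.31 to 0.51 for a one-third imatinib change is conditional on pilot SDs of 958 to 713 and correlation 0.5. It is not a ceiling. The metabolite is compatible with 1 SD as printed, but its mean and range are the same for pilot and CML patients, which may be a copying error.

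**What to change.** Change wording in Section 12.1 only; no extra patients or samples are needed.

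- Delete the statement that a 33% reduction equals 1 SD.
- Restate the power along these lines: *12 patients give 88% power for a change of 1 SD of the within-patient difference.*
- Give the SD assumed for that difference, with its source, for imatinib and the metabolite separately.
- Show power for a one-third imatinib change as a conditional range, for example 0.31 to 0.51 with pilot SDs of 958 to 713 and correlation 0.5, higher with a larger correlation or a smaller SD.
- State that the PK comparison will be reported with its confidence interval, and that a non-significant result will not be described as absence of an interaction.

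Also check the metabolite figures in Section 1.1.5 against their source before using them.

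The cost is a less favourable, or openly conditional, power statement for imatinib.
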